### 14.3.2.2. Laboratory Determinations

Actual values and change-from-baseline values for continuous data from laboratory determinations (serum chemistry, hematology, coagulation studies, and urinalysis) will be presented in listings. Categorical data measurements will be similarly summarized for the actual values. Laboratory measurements will be graded according to CTCAE, when applicable. The frequencies of the highest CTCAE grade observed will be displayed for each AE and for each starting dose level. Laboratory determinations categorized as in or out of normal range will be summarized in some cases using worst-case shift tables. Clinically significant (CS) or not clinically significant (NCS) criteria may be applied for out-of-range values.

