#### Patients to be Excluded (patients must not meet any of the following criteria)

- Women who are pregnant or intending to become pregnant during or within 3 months
  after the last dose of study drug; women who are breastfeeding; WOCBP and fertile
  men with a WOCBP partner not using and not willing to use a highly effective method
  of contraception
- Patients with known central nervous system (CNS) or leptomeningeal metastases, or spinal cord compression not controlled by prior surgery or radiotherapy, or patients with symptoms suggesting CNS involvement for which treatment is required
- 3. Patients with a malignancy other than that of epithelial origin
- 4. Phase 2a Expansion Cohorts ONLY: Patients with an active second malignancy or history of another malignancy within the last 2 years with the exception of:
  - Treated non-melanoma skin cancers
  - Treated carcinoma in situ
  - Controlled, superficial carcinoma of the bladder
  - T1a carcinoma of the prostate comprising < 5% of resected tissue and prostate specific antigen (PSA) within normal limits (WNL) since resection
- 5. Patients with any of the following hematologic abnormalities at baseline:
  - Hemoglobin < 9.0 g/dL
  - Absolute neutrophil count (ANC) < 1,500 per mm^3
  - Platelet count < 100,000 per mm^3
- 6. Patients with any of the following serum chemistry abnormalities at baseline:
  - Total bilirubin  $\geq 1.5 \times$  the upper limit of normal (ULN) for the institution
  - AST or ALT ≥ 3 × the ULN for the institution (≥ 5× ULN if due to hepatic involvement by tumor)
  - Serum creatinine  $\geq 1.5 \times ULN$
- Y. Patients with any of the following coagulation parameter abnormalities at baseline as

determined by the Investigator:

- PTT (or aPTT)  $\geq$  1.5 × ULN for the institution (> 3× ULN for the institution if anticoagulated)
- 8. Patients with:
  - Active thrombosis, or a history of deep vein thrombosis (DVT) or pulmonary embolism (PE) within 4 weeks prior to first study drug administration;
  - Active uncontrolled bleeding or a known bleeding diathesis
- 9. Patients with a significant cardiovascular disease or condition, including:
  - Congestive heart failure (CHF) currently requiring therapy
  - Need for anti-arrhythmic medical therapy for a ventricular arrhythmia or other uncontrolled arrhythmia (patients with controlled atrial fibrillation (heart rate [HR] < 90) for > 30 days prior to study entry are eligible)

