Laboratory abnormalities observed in greater than one patient were: asymptomatic platelet count decreases in 5 patients during Cycle 1, including a single Grade 4 event (at 270 mg/m² and meeting study DLT criteria for the dose cohort, see above), three Grade 3 events (at 120, 220, and 270 mg/m²), and one Grade 2 event (at 80 mg/m²); asymptomatic lipase elevations in 4 patients, including a single Grade 4 event during Cycle 8 (at 180 mg/m²), and three Grade 3 events, one during Cycle 1 (at 270 mg/m² and meeting study DLT criteria for the dose cohort, see above), one during Cycle 2 (at 220 mg/m²), one during Cycle 4 (at 80 mg/m²); and aspartate aminotransferase (AST) elevations of Grade 3 severity in 2 patients, reported during Cycle 1 for one patient, and Cycles 3, 4, and 5 for the second patient (at 220 and 180 mg/m², respectively).

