- Class III or IV cardiovascular disease according to the New York Heart Association's (NYHA) Functional Criteria (see **Appendix C**)
- History of acute coronary syndromes (including myocardial infarction [MI] and unstable angina), coronary angioplasty, stenting, or bypass grafting within 6 months prior to first study drug administration
- \*Assessment of LVEF will not be performed routinely in all patients. Patients with a history of CHF will have either a MUGA scan or echocardiogram at Screening. If LLN is not defined for a given institution, then LVEF must be  $\geq 50\%$
- 10. Patients with a significant ocular disease or condition, including:
  - History of ocular inflammatory disease
  - History of disorders of the cornea, including current evidence of keratitis at screening
- 11. Patients with a significant pulmonary disease or condition, including:
  - Significant symptomatic chronic obstructive pulmonary disease (COPD), as assessed by the Investigator
  - History or any current evidence on imaging studies prior to or during study of interstitial lung disease (ILD), pulmonary fibrosis
  - History of pulmonary inflammatory disease, pneumonitis, acute respiratory distress syndrome (ARDS)
- 12. Patients with a significant gastrointestinal (GI) disease or condition, including but not limited to:
  - History of inflammatory bowel disease
  - Diarrhea ≥ Grade 2 within 2 weeks prior to first study drug administration\*

- 13. Patients with non-healing wounds on any part of the body
- 14. Patients with a known or suspected hypersensitivity to any of the excipients of AVID100
- 15. Patients with any other serious/active/uncontrolled infection, any infection requiring parenteral antibiotics, or unexplained fever > 38°C within 2 weeks prior to first study drug administration
- 16. Patients with unresolved > Grade 1 toxicity\* associated with any prior antineoplastic therapy with the exception of persistent Grade 2 alopecia, peripheral neuropathy, decreased hemoglobin, hypomagnesemia, lymphopenia, and/or end-organ failure being adequately managed by hormone replacement therapy

\*AE assessments based on Common Terminology Criteria for Adverse Events [CTCAE Version 5.0]

\*Patients with recent Grade 2 diarrhea secondary to administration of oral contrast are allowed, provided symptoms have resolved prior to first study drug administration.

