# **FORBIUS**

Patient characteristics including race, ECOG PS, and age will be described using descriptive statistics. Frequency tables will summarize the incidence and type of treatment-related AEs by severity, experienced by patients who received at least 1 dose of study drug (Safety population).

Continuous variables, including baseline characteristics, will be summarized by reporting the number of observations, mean, standard deviation, median, minimum and maximum. Categorical/discrete variables will be summarized using frequency tables showing the number and percentage of patients within a particular category. Time-to-event data will be summarized using the Kaplan-Meier method. Withdrawals of patients from study medication and causes of death will also be reported as listings and summary tables.

Unless indicated otherwise, summary statistics will be reported for observed data only. Missing data will not be imputed. If a baseline value is missing, no change from baseline will be calculated. Baseline is defined as the last available observation prior to the first administration of study drug on Cycle 1/Week 1/Day 1.

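### The laboratory summary tables in Section 14.3.2.2 do not separate abnormality present at entry from worsening on drug

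*Combined protocol and SAP*

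**What the plan says.** Section 14.3.2.2 plans three outputs for laboratory data.

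- **Listings:** "Actual values and change-from-baseline values for continuous data from laboratory determinations" are to be presented as listings.
- **Grade table:** "The frequencies of the highest CTCAE grade observed will be displayed for each AE and for each starting dose level". No baseline grade and no worse-than-baseline condition is stated.
- **Shift table:** "Laboratory determinations categorized as in or out of normal range will be summarized in some cases using worst-case shift tables". There are two states, with no grade and no high or low direction.

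Section 14.3 does define a reference point: "Baseline is defined as the last available observation prior to the first administration of study drug on Cycle 1/Week 1/Day 1". Section 14.3.2.2 does not link it to the grade table.

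Eligibility lets in patients with abnormal values. Item 16 of Section 4.3.1 bars unresolved toxicity above Grade 1 from earlier therapy, "with the exception of persistent Grade 2 alopecia, peripheral neuropathy, decreased hemoglobin, hypomagnesemia, lymphopenia". For transaminases the synopsis excludes "AST or ALT ≥ 3 × the ULN for the institution (≥ 5× ULN if due to hepatic involvement by tumor", and item 6 of Section 4.3.1 sets the same limits. Values above normal but under those limits are therefore allowed.

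**The concern.** A dose-level laboratory table is read as a statement about the drug. If patients can enter with a graded abnormality and the table takes the highest grade regardless of entry status, part of what is read as toxicity was there before the first dose. If the companion shift table has only two states, a patient who starts out of range and gets worse shows no shift.

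Magnesium is the clearest case. Section 2.3.1.3 lists hypomagnesemia among the frequent or severe toxicities of anti-EGFR antibodies, and Section 4.3.1 admits patients who already have it at Grade 2. Transaminases are another: hepatotoxicity is the main DM1-related concern in Section 2.3.1.4, and raised values are allowed at entry.

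The adverse event tables do not fill the gap. Under Section 10.3.1 an abnormal laboratory value need not be reported as an AE unless it is clinically significant, is serious, needs intervention, or alters or ends treatment. The laboratory tables are the only planned summary of all graded values. Safety is a primary objective in both phases.

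**Working it through.** Section 14.3.2.2 states no rate or sample size, so there is no figure of the plan's to reproduce. The check is a reading of the tables, then an illustration.

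**Step 1. Pass three patients through the planned outputs.** The grade table is read here as covering graded laboratory parameters.

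| Patient | In/out shift table | Highest-grade table | Change-from-baseline listing |
|---|---|---|---|
| A: enters with Grade 2 low magnesium, unchanged | out to out | Grade 2 | no change |
| B: enters with Grade 2 low magnesium, falls to Grade 3 | out to out | Grade 3 | fall shown |
| C: enters in range, falls to Grade 2 | in to out | Grade 2 | fall shown |

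The grade table cannot tell A from C. The shift table cannot tell A from B. Two separate summary tables cannot be joined patient by patient, so only the listing resolves all three. Similarly, a patient with hepatic tumour who enters with AST at 4 × ULN and rises to 20 × ULN is out to out.

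**Step 2. A cohort example.** Section 14.2 plans 15 patients per cohort or mTNBC subgroup. Suppose 6 of the 15 enter with Grade 2 hemoglobin and 3 of those 6 fall to Grade 3. Among these 6:

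- shift table: 0 shifts;
- highest-grade table: 3 at Grade 3 and 3 at Grade 2, so 3 + 3 = 6 graded;
- baseline grade by worst grade: 3 worsened, 3 unchanged.

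**Step 3. Size of the entry effect on the grade table.** Let b be the share of patients entering with a graded abnormality in one analyte, n the number treated, and suppose the drug has no effect. The expected count is n × b, and the chance of at least one is 1 − (1 − b)^n. The documents give no b, so 10%, 30% and 50% are assumptions. The second denominator, n = 60, is the planned Phase 2a total. It matters because the table is by starting dose and all Phase 2a patients start at 220 mg/m².

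| n | b | n × b | Chance of at least one |
|---|---|---|---|
| 15 | 10% | 1.5 | 0.794 |
| 15 | 30% | 4.5 | 0.995 |
| 15 | 50% | 7.5 | about 1.00 |
| 60 | 10% | 6.0 | 0.998 |
| 60 | 30% | 18.0 | about 1.00 |
| 60 | 50% | 30.0 | about 1.00 |

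If only grades above baseline are counted, the figure is 0 in every row by construction.

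**Step 4. Size of the effect on the shift table.** Let b now be the share out of range at entry, again assumed. If worsening is unrelated to entry status, the table can show at most 1 − b of the patients who worsen: 90%, 70% or 50% for the same three values.

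**The case against.** The case for leaving the section alone has real substance.

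- **Worsening is not lost.** Change from baseline is listed per patient, and with about 15 patients per cohort a listing can be read. A patient who worsens also appears at the final grade in the grade table. This stands: the loss is confined to the shift table, which is planned only for some cases.
- **The grade table may already use baseline.** It is displayed for *each AE*. Section 10.3 captures events that are new or worse than baseline, and Section 10.3.1 excludes pre-existing conditions unless they worsen. If AE means a reported event, patient A is not counted. This reading is possible. However, the sentence sits in the laboratory section directly after the statement that laboratory measurements will be graded, so the text does not settle it.
- **Some criteria refer to baseline.** The transaminase component of the liver DLT in Section 6.8.3 uses a multiple of baseline when the value is raised at entry, and the Grade 3 creatinine criterion in Section 9.1 includes one. This stands, and it rules out saying that no laboratory grade has a baseline reference. It also shows that the protocol recognises the issue elsewhere.
- **Other entry rules limit abnormal values.** No numeric limit is set for lipase or ALP, but item 18 of Section 4.3.1 excludes clinically significant laboratory abnormalities that, in the investigator's opinion, compromise safety or study evaluation. Item 16 does not list lipase or ALP among its exceptions. A Grade 4 platelet count (below 25,000 per mm³) cannot be an entry value, since counts below 100,000 per mm³ are excluded.
- **Detail is left to a later SAP.** Section 14.3 says so. But Section 14.3.2.2 already names the displays, and they will carry forward unless changed.

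A reader might also infer that the dose decision is compromised, because laboratory signals drove it. The documents do not support that. Section 2.3.2.1 reports these signals patient by patient with grade and cycle, for example "asymptomatic lipase elevations in 4 patients, including a single Grade 4 event during Cycle 8". Table 1 lists platelet, lipase and AST events as treatment-related AEs, and Section 6.8.3 requires a DLT to be judged associated with study drug. The 220 mg/m² decision in Section 2.6 rests on those individual events, not on the tables at issue.

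**Conclusion.** The point holds for the two summary tables as written. The highest-grade frequency has no stated baseline condition, subject to the ambiguity in *each AE*, and the two-state shift table cannot show worsening in patients already out of range. Eligibility admits such patients, so dose-level laboratory toxicity rates may be misread.

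The size cannot be fixed from the documents. Under assumed entry shares of 10% to 50%, a 15-patient cohort with no drug effect would show on average 1.5 to 7.5 graded patients per analyte. That rests on the laboratory-parameter reading of the grade table and on grades that are not themselves relative to baseline.

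It would go too far to say that the rates are wrong, or that pre-existing and new abnormality cannot be separated at all: the listings separate them. DLTs, the MTD, the RP2D and sample size are unaffected. This is a reporting weakness that should be corrected before the SAP is final, not a flaw in the design.

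**What to change.** In Section 14.3.2.2 and in the SAP:

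1. Replace the in/out-of-range shift table with baseline CTCAE grade by worst post-baseline grade, with low and high directions separate, by starting dose level and by Phase 2a cohort. Cover the key hematology and chemistry analytes, at least platelets, ANC, hemoglobin, lymphocytes, AST, ALT, bilirubin, ALP, lipase, amylase, creatinine, magnesium, potassium and calcium.
2. Count as treatment-emergent only a grade above the baseline grade, using the baseline definition in Section 14.3.
3. State whether *each AE* means a graded laboratory parameter or a reported adverse event.

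The cost is a few lines of text and a small amount of standard programming. The panels in Sections 7.2.6 and 7.2.7 already collect the values at screening and on treatment, so no new assessment is needed.

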### 14.3.2.3. Vital Signs, Body Weight, Physical Exam Findings

Actual values and change-from-baseline values for vital signs and body weights, as well as physical examination findings, will be summarized descriptively.

### **14.3.2.4. ECG Findings**

Descriptive statistics of ECG observations will be presented. The frequency and percentage of ECG results will be summarized for the following ECG measurements: heart rate, PR interval, QRS duration, QT interval and QTc interval. The heart rate-corrected QT interval (QTc), indicating repolarization time, will be calculated. T-wave and ST-segment ECG abnormalities will be graded based on definitions in the NCI Common Toxicity Criteria (CTC). Additional details regarding the ECG analyses will be provided in the SAP.

#### 14.3.2.5. Other Safety Data

Concomitant medications and findings in physical examinations, pulmonary function tests, and anti-drug antibody analyses (ADA) will be summarized in text as recorded in the eCRF, and as made available from an independent central assay laboratory, in the case of ADA data.

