## 7.3.1 Ophthalmology Examination

(To include slit lamp evaluation, tests to evaluate corneal integrity and visual acuity assessment)

- Screening
- End of Cycle 2\*,\*\*
- EOT\*\*
- As clinically indicated

\*When evaluating QTc, baseline should be considered the ECG immediate preceding the start of study drug infusion on the day of assessment.

\*\*In the event of significant electrolyte abnormalities, the evaluation frequency should be increased to include additional evaluations between the scheduled assessments, as clinically indicated

\*End of Cycle assessments may be conducted at any time during the week prior to Day 1 of the next cycle.

\*\*May be combined if patient discontinues treatment at End of Cycle 2

Note: See Appendix H (Recommendations for Management of Keratitis and Rash) for dose modification instructions for keratitis (corneal inflammation/ulceration)

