# 7.3.3 Pulmonary Function Testing

(PTF to include spirometry and diffusing capacity [DLco] to assess for evidence of pulmonary fibrosis. Spirometry assessments are to include but are not limited to: forced vital capacity [FVC], forced expiratory volume in 1 second [FEV1], forced expiratory flow 25% to 75% [FEF25-75], functional residual capacity [FRC], residual volume [RV], and total lung capacity [TLC].)

- Screening
- EOT
- As clinically indicated

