### 9.1. Criteria for Treatment Discontinuation

Patients will be discontinued from further treatment with study drug in the event of any of the following:

- 1. Patient must be permanently discontinued in the event of any major, potentially irreversible organ system DLT, including:
  - Pulmonary toxicity defined as:
    - o Evidence of pulmonary fibrosis, any grade
    - o Reduction of forced vital capacity (FVC) or DLco  $\geq$  Grade 3
  - Neurotoxicity defined as peripheral neuropathy ≥ Grade 3
  - Any ocular toxicity  $\geq$  Grade 3
  - Nephrotoxicity defined as:
    - Acute kidney disease  $\geq$  Grade 3 (i.e., creatinine  $> 3 \times$  baseline or > 4.0 mg/dL)
    - o Chronic kidney disease ≥ Grade 3 (i.e., estimated glomerular filtration rate [eGFR] or creatinine clearance [CrCl] 29-15 mL/min/1.73 m²)
    - o Proteinuria  $\geq$  Grade 3 (i.e.,  $\geq$  3.5 g/24 hours)
  - Hepatotoxicity suggestive of drug-induced liver injury, as characterized by the following 3 criteria:
    - AST and/or ALT elevation  $> 3 \times ULN$  (or  $> 3 \times$  baseline if elevated at study entry as allowed by study eligibility criteria; see **Section 4.3.1** #7)
    - Total bilirubin  $> 2 \times ULN$  without initial findings of cholestasis (i.e., no elevation in serum ALP)
    - No explanation for the above findings, such as: viral hepatitis A, B, or C; preexisting or acute liver disease; or another drug capable of causing the observed injury

Adapted from: Hy's Law. Drug-induced liver injury: premarketing clinical evaluation. Guidance for Industry. U.S. Department of HHS, FDA, CDER, CBER, 2009.

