# APPENDIX A Study Assessments

			TABI	LE 7:	: STU	J DY A	ASSE	SSMEN	TS SCH	IEDULE	,				
			YCLE 1				CYCL			BSEOUEN		EOT < 10d	1M FUP*	Extended	As
STUDY ASSESSMENTS	Screen	D1	D2	D4 +/- 1d	D8	D1	D8	End of Cycle 2	D1	D8	End of Even Number Cycles d	after decision to dis-continue	30 d (+7) after last dose	Follow Up* if OR or SD at EOT	Clinically Indicated
CONSENT AND MEDICAL HISTORY															
Informed Consent  / Eligibility Assessment	X														
Past Medical History	X														
History of Primary Malignancy 	X														
SAFETY ASSESSMENTS (1) (screening asses	sments withi	n 14 days prior to	o first sti	ıdy dru	g dose										
Medication Survey 	X									0 days after					
AE Assessments 			t through	30 day	ys after l	ast dose	; throug	h 3 months	or 6 months	to 2 years)	follow-up if associa				 
ECOG PS Evaluation	Х	X a				X			X			х	X		X
Phase 1a: Vital Signs 	x	SOI; EOI; 2, 4h after EOI	х	х		х			x			x	х		х
Phase 2a: Vital Signs 	X	SOI, EOI				X			X			х	X		X
Physical Exam/to include weight and	X	x a				х			x			x	х		x
pulmonary assessment 															_ ^
Hematology Panel 	X	x a		X	X	X	X		X	X		X	X		X
Serum Chemistry Panel 	X	x a		X	X	X	X		X	X		X	X		X
Coagulation Panel 	X	X a		X	X	X	X		X	X		х	X		Х
Urinalysis 	X	x a		X	X	X	X		X	X		х	X		Х
ADA to AVID100 		X				X			X			х	X		xe
Pregnancy Testing  (w/in 2 days of I st dose)	X	X										х			Х
ECG (12-lead) 	x	SOI, EOI, 30 min after EOI										x			x
SAFETY ASSESSMENTS (2) (screening asses	sments withi	n 28days (+/- 2)	prior to	first sti	udy druį	g dose p	rovided	no antineo	plastic thera	py has been	delivered between a	ssessment and	first dose of s	tudy drug)	
Ophthalmology Exam 	X										End of C2 only	X			х
MUGA Scan or Echo 	X											X			X
Pulmonary function tests 	X											x			X
Chest radiography (PA and lateral)	X											x			X
DISEASE ASSESSMENTS (screening assessm	ents within 2	28 days (+2d) prie	or to first	t study	drug do	se)									
Phase 1a only: Document EGFR positivity 	optional														
Phase 2a only: Document EGFR positivity 	required														

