# **FORBIUS**

- baseline; or c) decreased by 20 msec under baseline.
- 14. Ophthalmology Examination: To include slit lamp evaluation, tests to evaluate corneal integrity, and visual acuity assessment. End of C2 and EOT may be combined if patient discontinues treatment at End of C2
- 15. MUGA Scan or Echocardiogram: For measurement of LVEF; to be performed ONLY in patients with a history of CHF, individual patients should be followed with the same testing procedure throughout the study.
- 16. Pulmonary Function Tests: To include spirometry and diffusing capacity (DLCO) to assess for evidence of pulmonary fibrosis (spirometry assessments are to include but are not limited to: forced vital capacity [FVC], forced expiratory volume in 1 second [FEV1], forced expiratory flow 25% to 75% [FEF25-75], functional residual capacity [FRC], residual volume [RV], and total lung capacity [TLC])
- 17. EGFR status determination/documentation of EGFR positivity by IHC:
  - Phase 1a: Optional (Local or Central\*)
  - Phase 2a: Required (Central Lab\*); tumor must be EGFR-positive for patient to be eligible for enrollment
  - \*The trial site will prescreen patients for EGFR Tumor Status Determination before entering patients into screening for the treatment portion of the trial. The site should use a separate prescreening informed consent form. Prescreening may be performed outside the 28 (+ 2) day screening period to allow adequate turnaround time for receipt of results, provided separate informed consent has been obtained.
- 18. Tumor Marker Measurement (Phase 1a only): As indicated by tumor type.

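### Lung function is tested at Screening and End of Treatment to look for fibrosis, but Section 14.3.2.5 plans only a narrative summary, so an asymptomatic group decline in FVC or DLco would not be quantified

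*Combined protocol and SAP*

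**What the plan says.** **Collection.** Section 7.3.3 schedules pulmonary function tests at Screening, at EOT and when clinically indicated. The stated content and purpose are "PTF to include spirometry and diffusing capacity [DLco] to assess for evidence of pulmonary fibrosis". FVC, FEV1, mid-expiratory flow and lung volumes are listed. Table 7 in Appendix A gives the same timing.

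**Use for the individual patient.** Section 9.1 lists "Reduction of forced vital capacity (FVC) or DLco" at Grade 3 or worse among the pulmonary toxicities that require permanent discontinuation.

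**Planned reporting.** Section 14.3.2.5 states that "pulmonary function tests, and anti-drug antibody analyses (ADA) will be summarized in text as recorded in the eCRF". Concomitant medications and physical examination findings are in the same sentence.

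**Reporting of other safety measures.** Section 14.3.2.3 promises "Actual values and change-from-baseline values for vital signs and body weights", summarized descriptively. Section 14.3.2.4 gives ECG intervals descriptive statistics and frequencies. Section 14.3.2.2 gives laboratory results highest-grade frequencies and, in some cases, worst-case shift tables.

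**Eye examinations.** Section 7.3.1 schedules an ophthalmology examination at Screening, End of Cycle 2 and EOT: "To include slit lamp evaluation, tests to evaluate corneal integrity and visual acuity assessment". No subsection of Section 14 names these data.

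**The concern.** Safety is part of the Phase 2a primary objective (Section 3.2.1), and lung toxicity is a harm the protocol takes particular trouble over. Section 2.3.1.3 names pulmonary fibrosis and interstitial lung disease as toxicities of anti-EGFR antibodies. Section 2.4.2 cites one case of treatment-related pneumonitis in Phase 1a among its reasons for the lung monitoring.

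FVC and DLco are the continuous lung measurements collected for this purpose. A narrative account of individual findings can describe the patient whose DLco collapsed. It cannot show that most patients lost a modest amount. If that happened, the study report would contain nothing from which a reader could see it or judge its size, although the data would be in the database.

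**Working it through.** The plan gives no figure to reproduce. The check is whether any planned output would quantify an asymptomatic fall in FVC or DLco.

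**Step 1. Routes by which such a fall could reach the report**

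| Route | Where | Would it quantify an asymptomatic fall in FVC or DLco? |
|---|---|---|
| Pulmonary function summary | 14.3.2.5 | No. Text only; no change from baseline, no grade table |
| Adverse-event tables by maximum CTCAE grade | 14.3.2.1 | Only if the fall is reported as an adverse event |
| Rule for reporting test abnormalities as adverse events | 10.3.1 | Not required unless clinically significant, an SAE, needing intervention, or changing or stopping therapy |
| Vital signs, including oxygen saturation | 7.2.4, 14.3.2.3 | No. A different lung measure, though it does get change from baseline |
| Chest imaging at every disease assessment | 7.4.3 | No. Detects structural change, not FVC or DLco |
| General rule for continuous variables (n, mean, SD, median, range) | 14.3 | Unclear. Names no lung test, promises no change from baseline for them, and 14.3.2.5 is the more specific rule |

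No route commits the plan to a group summary of change in FVC or DLco.

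**Step 2. The same check for the eye**

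Appendix H says that even Grade 1 keratitis leads to treatment. Section 10.3.1 makes an abnormality needing intervention reportable, and Section 14.3.2.1 tabulates reported events by grade. Graded keratitis therefore does reach the tables. Only untreated minor corneal change and visual acuity lack a planned summary.

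**Step 3. What a paired summary could show**

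The documents give no SD for change in DLco. Assume 10 to 15 percentage points. The half-width of a 95% confidence interval for mean change is t × SD / √n. The last column is the chance that this interval excludes zero if the true mean loss is 5 points (paired t calculation).

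| Pairs (n) | SD | t | Half-width | Chance of excluding zero |
|---|---|---|---|---|
| 60 | 10 | 2.001 | 2.001 × 10 / 7.746 = 2.6 | 97% |
| 40 | 15 | 2.023 | 2.023 × 15 / 6.325 = 4.8 | 54% |
| 15 | 10 | 2.145 | 2.145 × 10 / 3.873 = 5.5 | 44% |
| 15 | 15 | 2.145 | 2.145 × 15 / 3.873 = 8.3 | 22% |

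The 40 and 60 are assumptions: 60 is the planned Phase 2a total with every patient tested twice. Fifteen is the planned size of the SCCHN and Sq-NSCLC cohorts. The later adverse-event table in Section 2.3.2 covers 13 patients (data as of 15 April 2020). At n = 13 the half-width is 2.179 × 10 / 3.606 = 6.0 to 2.179 × 15 / 3.606 = 9.1 points. A paired summary is therefore descriptive, and within a single cohort it is imprecise.

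**The case against.** **The plan watches the lung in other ways.** Oximetry is summarized as change from baseline, and the chest is imaged at each disease assessment. Drug-associated fibrosis of any grade is a dose-limiting toxicity (Section 6.8.3). Organ-damage toxicity in two or more patients closes an expansion cohort to accrual (Section 6.6.3.3). A Grade 1 reduction in forced expiratory flow already appears in the later adverse-event table, so mild changes are sometimes reported. All of this stands, and it confines the gap to asymptomatic decline that no one reports.

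**A text summary need not exclude statistics.** Physical examination findings are assigned to text in Section 14.3.2.5 and to a descriptive summary in Section 14.3.2.3. Section 14.3 also has a general rule for continuous variables and defers detail to an SAP to be finalized before database lock. This is a fair caution: the finding is that the supplied documents plan no such summary, not that none will be produced. But Section 14.3.2.4 says further ECG detail will follow in the SAP, and Section 14.3.2.5 says nothing comparable.

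**EOT values are hard to interpret.** The trial is uncontrolled, one cohort has squamous lung cancer, and progression is itself a reason to stop treatment. A mean fall at EOT cannot separate drug effect from disease. That limits interpretation and must be stated beside the table. It is not a reason to leave the data untabulated.

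**Two stronger readings are tempting.** One is that a paired summary would detect a mean DLco loss of 5 points. The documents do not support this: the SD and number of pairs are assumptions, and at SD 15 the chance is 54% with 40 pairs and about 22% with 15. The other is that corneal harm escapes the adverse-event tables. It does not, because even Grade 1 keratitis is treated and so becomes reportable.

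**Conclusion.** The point holds as a reporting gap. Pulmonary function data collected to look for fibrosis, and tied to a discontinuation criterion, are assigned a text summary, while vital signs, ECGs and laboratory values get quantitative or graded summaries. Together with the reporting threshold in Section 10.3.1, this leaves an asymptomatic group decline in FVC or DLco unquantified. Overt lung harm would still be captured.

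No numerical size can be attached, because the documents give neither a variability for the change nor an expected number of paired tests. The conclusion rests on reading Section 14.3.2.5 as the specific rule for these data and on the supplied documents alone; an SAP not seen here could already close the gap. No objective, dose decision or sample size is affected. The missing eye summary is minor.

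**What to change.** In Section 14.3.2.5, or in the SAP before database lock, replace the text summary of pulmonary function with:

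- actual values and change from Screening to EOT, and to the worst on-study value, for FVC and DLco, using the descriptive statistics already listed in Section 14.3 and naming the unit;
- a shift table from baseline to worst CTCAE grade for FVC and DLco;
- both presented pooled at the recommended Phase 2 dose, in line with Section 14.1, and by dose level or cohort;
- the number of patients with paired tests and the number without an EOT test, since Section 14.3 does not impute missing data;
- a note that disease progression confounds EOT values in an uncontrolled trial, and that tests done only when clinically indicated make the worst value a selected one.

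These tables are descriptive, so they respect the statement in Section 14.1 that no inferential tests will be done. As an optional addition only, give a shift listing of visual acuity and corneal findings from Screening to End of Cycle 2 and EOT.

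The cost is SAP wording and a few tables from data already scheduled. No visit, test, dose, stopping rule or sample size changes.
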